## 6. ADVERSE EVENT REPORTING

### Definitions

The following definitions of terms apply to this section:

Adverse event: Any untoward medical occurrence associated with the use of a drug in humans, whether or not considered drug related.

Life-threatening adverse event or life-threatening suspected adverse reaction: An adverse event or suspected adverse reaction is considered "life-threatening" if, in the view of either the investigator or sponsor, its occurrence places the patient or subject at immediate risk of death. It does not include an adverse event or suspected adverse reaction that, had it occurred in a more severe form, might have caused death.

Serious adverse event or serious suspected adverse reaction: An adverse event or

suspected adverse reaction is considered "serious" if, in the view of either the investigator or sponsor, it results in any of the following outcomes: death, a life-threatening adverse event, inpatient hospitalization or prolongation of existing hospitalization, a persistent or significant incapacity or substantial disruption of the ability to conduct normal life functions, or a congenital anomaly/birth defect. Important medical events that may not result in death,

be life-threatening, or require hospitalization may be considered serious when, based upon appropriate medical judgment, they may jeopardize the patient or subject and may require medical or surgical intervention to prevent one of the outcomes listed in this definition. Examples of such medical events include allergic bronchospasm requiring intensive treatment in an emergency room or at home, blood dyscrasias or convulsions that do not result in inpatient hospitalization, or the development of drug dependency or drug abuse.

**Suspected adverse reaction:** Any adverse event for which there is a reasonable possibility that the drug caused the adverse event. Suspected adverse reaction implies a lesser degree of certainty about causality than adverse reaction, which means any adverse event caused by a drug.

Adverse reaction means any adverse event caused by a drug. Adverse reactions are a subset of all suspected adverse reactions where there is reason to conclude that the drug caused the event.

**Unexpected adverse event or unexpected suspected adverse reaction:** An adverse event or suspected adverse reaction is considered "unexpected" if it is not listed in the investigator brochure or is not listed at the specificity or severity that has been observed; or, if an investigator brochure is not required or available, is not consistent with the risk information described in the general investigational plan or elsewhere in the current application, as amended. For example, under this definition, hepatic necrosis would be unexpected (by virtue of greater severity) if the investigator brochure referred only to elevated hepatic enzymes or hepatitis. Similarly, cerebral thromboembolism and cerebral vasculitis would be unexpected (by virtue of greater specificity) if the investigator brochure listed only cerebral vascular accidents. "Unexpected," as used in this definition, also refers to adverse events or suspected adverse reactions that are mentioned in the investigator brochure as occurring with a class of drugs or as anticipated from the pharmacological properties of the drug, but are not specifically mentioned as occurring with the particular drug under investigation.

#### Eliciting AE Information

Research subjects will be routinely questioned about AEs at study visits.

#### Recording Requirements

All observed or volunteered adverse events (serious or non-serious) and abnormal test findings, regardless of study group or suspected causal relationship to the study drug(s) will be recorded in the subjects' case histories. For all adverse events, sufficient information will be pursued and/or obtained so as to permit 1) an adequate determination of the outcome of the event (i.e., whether the event should be classified as a *serious adverse event*) and; 2) an assessment of the causal relationship between the adverse event and the study drug(s).

AEs or abnormal test findings felt to be associated with the investigational drug or study treatment(s) will be followed until the event (or its sequelae) or the abnormal test finding resolves or stabilizes at a level acceptable to the Sponsor-Investigator.

#### Abnormal Test Findings

An abnormal test finding will be classified as an *adverse event* if one or more of the following criteria are met:

- The test finding is accompanied by clinical symptoms.
- The test finding necessitates additional diagnostic evaluation(s) or medical/surgical intervention; including significant additional concomitant drug treatment or other therapy.

**Note:** simply repeating a test finding, in the absence of any of the other listed criteria, does not constitute an AE.

- The test finding leads to a change in study dosing or discontinuation of subject participation in the clinical study.

#### REPORTING OF SERIOUS ADVERSE EVENTS

All events meeting the definition of a serious adverse event, from the date of first dose of study drug until 30 days after last dose, should be reported according to the departmental SAE checklist and SAE form. The initial SAE form should be sent to the following within 24 business hours / 1 business day of the Principal Investigator becoming aware:

1. [name]
2. [contact]
3. Local Institutional Review Board when reporting requirements are met.
4. Pfizer Safety @ [[contact]](mailto:[contact])

In addition to completing appropriate patient demographic and suspect medication information, the report should include as applicable the following information that is available at the time of report within the Sections B and C of the departmental SAE form:

- CTCAE(5.0) term(s) and grade(s)
- current status of study drug
- all interventions to address the AE (testing and result, treatment and response)
- hospitalization and/or discharge dates
- event relationship to study drug

#### Follow-up reports:

Additional information may be added to a previously submitted report by adding to the original departmental SAE form and submitting it as follow-up or creating supplemental summary information and submitting it as follow-up with the original departmental SAE form.

#### Special Interest Serious Adverse Events

The following events also require reporting to Pfizer at the fax number provided above.

1. Exposure during Pregnancy, Exposure during Lactation, Occupational Exposure, and Lack of Effect. Even though there may not be an associated SAE, exposure to the Pfizer drug product during pregnancy, exposure to the Pfizer drug product during lactation, and occupational exposure to the Pfizer drug product are reportable, and lack of effect of the Pfizer drug product may also be reportable. The term SAE is understood to include exposure during pregnancy, exposure during lactation, occupational exposure, and reportable instances of lack of effect.
2. Hy's Law Cases. Cases of potential drug-induced liver injury as assessed by laboratory test values are reportable. If a Subject develops abnormal lab values in aspartate transaminase (AST) or alanine transaminase (ALT) or both, concurrent with abnormal elevations in total bilirubin and no other known cause of liver injury, that event would be classified as a Hy's Law Case. The term SAE is understood to include Hy's Law Cases.

## 7. DATA SAFETY MONITORING PLAN

Investigator/Sub-investigators, regulatory, CRS management, clinical research coordinators, clinical research associates, data managers, and clinic staff meet regularly in the disease center Data Safety Monitoring Board (DSMB) to review and discuss study data to include, but not limited to, the following:

- serious adverse events
- subject safety issues
- recruitment issues
- accrual
- protocol deviations
- unanticipated problems
- breaches of confidentiality

Minutes from the disease center DSMB meetings are available to those who are unable to attend in person.

All toxicities encountered during the study will be evaluated on an ongoing basis according to the NCI Common Toxicity Criteria Version 5.0. All study treatment associated adverse events that are serious, at least possibly related and unexpected will be reported to the IRB. Any modifications necessary to ensure subject safety and decisions to continue or close the trial to accrual are also discussed during these meetings. If any literature becomes available which changes the risk/benefit ratio or suggests that conducting the trial is no longer ethical, the IRB will be notified in the form of an Unanticipated Problem submission and the study may be terminated.

All study data reviewed and discussed during these meetings will be kept confidential. Any breach in subject confidentiality will be reported to the IRB in the form of an Unanticipated Problem submission. The summaries of these meetings are forwarded to the UPMC Hillman Cancer Center DSMC which also meets monthly following a designated format.

For all research protocols, there will be a commitment to comply with the IRB's policies for reporting unanticipated problems involving risk to subjects or others (including adverse events). DSMC progress reports, to include a summary of all serious adverse events and modifications, and approval will be submitted to the IRB at the time of renewal.

Protocols with subjects in long-term (survival) follow-up or protocols in data analysis only, will be reviewed bi-annually.

Both the UPMC Hillman Cancer Center DSMC as well as the individual disease center DSMB have the authority to suspend accrual or further investigate treatment on any trial based on information discussed at these meetings.

All records related to this research study will be stored in a locked environment. Only the researchers affiliated with the research study and their staff will have access to the research records.

## **8. STUDY EVALUATION, TREATMENT SCHEMA AND FLOW CHART**

Pre-treatment evaluation	
	Within last 6 weeks from day of consent
Anti-Hepatitis C antibody and if positive HCV RNA PCR	X

Hepatitis B surface antigen	X
	Within 14 days from day of consent
Medical history and physical examination	X
Height, weight, BSA, ECOG performance status	X
Toxicities from prior therapies	X
Cardiac echocardiogram	X
Bone marrow biopsy and aspiration	X
Urine $\beta$ HCG in women $\leq$ 60 years old (pregnancy test)	X
PT/INR, PTT	X
Complete metabolic panel (Na, K, Cl, CO 2 , glucose, BUN, Cr, Ca, total protein, albumin, total bilirubin, AST, ALT and alkaline phosphatase)	X
Magnesium, Phosphorous, Uric Acid, LDH	X
CBC with differential	X
Urinalysis	X
Electrocardiogram (12 lead)	X
Chest radiograph	X
CT Chest, Abdomen and/or Pelvis if indicated	X

Treatment Schema						
	Day 1	Day 2	Day 3	Day 4	Day 5	Day 6
Mitoxantrone	X	X	X	X	X	
Etoposide *	X	X	X	X	X	
Gemtuzumab ozogamicin **						X

\* Dose modification of etoposide for patients who develop elevated total bilirubin and/or AST or decrease in creatinine clearance

Adverse event	Dose modification of etoposide
CrCl 10 – 50 ml/min	administer 75% of normal dose
CrCl < 10 ml/min	administer 50% of normal dose
CrCl <50 ml/min AND Total bilirubin >3 mg/dL or AST >3 times ULN	Hold etoposide

\*\*If enrolled patients on day 6 of therapy have levels of aspartate aminotransferase (AST)  $\geq 2.5 \times$  UNL or alanine aminotransferase (ALT)  $\geq 2.5 \times$  UNL or total bilirubin  $\geq 2 \times$  ULN the administration of GO will be on hold until recovery of total bilirubin to less than or equal to  $2 \times$  ULN and AST and ALT to less than or equal to  $2.5 \times$  ULN prior to each dose. Daily values of LFTs will be obtained. The GO dose can be delayed up to the 10th day after the initiation of therapy due to toxicity or unexpected events (ie infection). Doses of GO will be capped at 4.5mg. Administration of a FLT3 inhibitor will be prohibited until CR is achieved. The use of a FLT-3 inhibitor is not prohibited after CR has been achieved for patients with FLT3-ITD or FLT-TKD mutations.

ON STUDY EVALUATION	TIMING
History and physical examination	Daily during the hospital stay at UPMC Shadyside Hospital and then weekly as outpatient for 4 weeks, and then every 2 weeks until count recovery
CBC with differential	CBC with differential will be performed daily during the inpatient stay and weekly as outpatient until count recovery

Complete metabolic panel including LFTs	Complete metabolic panel including liver function tests (LFTs) will be performed daily during the admission. After discharge, they will be followed weekly as outpatient until count recovery
Bone marrow aspiration and biopsy (to evaluate disease status)	At least 7 days after the completion of treatment
Weight	Daily (if clinical possible) while in hospital and during each visit outpatient

Bone marrow biopsy, aspirate with flow cytometry studies, cytogenetics and molecular studies will be performed no earlier than 7 days after the completion of treatment. Once hematopoietic recovery has been achieved patients will undergo bone marrow biopsy and/or aspiration for disease evaluation which can be performed in the inpatient or outpatient setting. If the bone marrow is consistent with morphologic complete remission, minimal residual disease testing will be performed with flow cytometry. If on diagnosis the NPM1 mutation was detectable by PCR or next-generation sequencing then NPM1 PCR will be performed as well if morphologic complete remission is achieved. If hematopoietic recovery has not been achieved by 5 weeks after the completion of therapy bone marrow biopsy and/or aspiration for disease evaluation will be performed.

Study Flow Chart										
Screening Period		Treatment Days						Post-treatment		
	Main Study Screening	1	2	3	4	5	6	Daily during Inpatient stay	Follow Up Visits	Survival Follow up a
Scheduling Window (Days)	-14 to 0	Can delay each dose up to 3 days.			Up to 5 days from the last dose of etoposide/mitoxantrone b				Weekly c	
Informed Consent	X									
Inclusion/Exclusion Criteria	X									

Medication Review d	X	X	X	X	X	X	X	X		
Trial Treatment Administration		X	X	X	X	X	X			
Post-study anticancer therapy status										X
Survival Status										X
Review Adverse Events	X (from 1st induction therapy)	X	X	X	X	X	X	X	X	
Full Physical Examination	X									X
Directed Physical Examination		X	X	X	X	X	X	X		
Vital Signs and Weight	X	X	X	X	X	X	X	X	X	
ECOG Performance Status	X	X	X	X	X	X	X	X	X	
Urine or Serum β-HCG	X									
PT/INR and aPTT	X e									
CBC with differential	X e	X	X	X	X	X	X	X	X f	
Comprehensive Serum Chemistry Panel g	X e	X	X	X	X	X	X	X	X f	
Magnesium, Phosphorus, Uric Acid, LDH	X e	X	X	X	X	X	X	X		
Urinalysis	X e									
Chest Radiograph	X e									
Echocardiogram	X h									
EKG	X e									
Bone Marrow Biopsy	X i								X j	
Archival or Newly	X									
Obtained Tissue Collection										

a Survival will be assessed daily during inpatient stays and then in the follow up visits. After the assessment of the recovery marrow or the marrow after 5 weeks from the completion of therapy patients will be followed remotely from chart review to evaluate the disease-free survival and overall survival. If information cannot be obtained from the chart, patients may be contacted by telephone. b Administration of a FLT3 inhibitor will be prohibited until CR is achieved. The use of a FLT-3 inhibitor is not prohibited after CR has been achieved for patients with FLT3-ITD or FLT-TKD mutations.

c After discharge the patient will be followed weekly for 4 weeks and then every 2 weeks until count recovery (defined as ANC  $\geq$  1000 with or without PLT  $\geq$  100,000). If patients develop grade 3 or 4 nonhematologic toxicity during their treatment they will be followed weekly after discharge until resolution of toxicity or improvement to grade 2 or less. There is  $\pm$  4 days window for each visit. d Medication review will be performed from the day of screening until the day of discharge. e All screening laboratory assessment must occur within 14 days after consent is signed. f After discharge, CBC with differential and complete metabolic panel will be obtained weekly until count recovery (defined as ANC  $\geq$  1000 with or without PLT  $\geq$  100,000). g Includes Na, K, Cl, HCO3, BUN, Cr, glucose, Ca, total protein, albumin, total bilirubin, AST, ALT, alkaline phosphatase. h Transthoracic Echocardiogram must be performed after the administration of 7 days of cytarabine with 3 days of idarubicin and before the first day of the study treatment. i Bone marrow with persistent disease as described in eligibility criteria section and CD33 expression in  $\geq$  30% leukemic blasts on the bone marrow. j Bone marrow biopsy and/or aspirate will be performed no earlier than 7 days after the therapy completion to evaluate disease response. Bone marrow biopsy/aspiration to test for remission once hematopoietic recovery has been achieved will be performed in the inpatient or outpatient setting. If hematopoietic recovery has not been achieved by 5 weeks after the completion of therapy bone marrow biopsy/aspiration for disease evaluation will be performed. If the recovery bone marrow is consistent with morphologic complete remission, minimal residual disease testing will be performed with flow cytometry. If at AML diagnosis the NPM1 mutation was detectable by PCR or next generation sequencing then NPM1 PCR will be performed as well. k Blood will be collected prior to the initiation of therapy with mitoxantrone and etoposide, prior to the initiation of therapy with GO, after the administration of GO and weekly while in the hospital. Blood and bone marrow aspirate will be collected at the time of bone marrow evaluation following therapy and at the time of bone marrow evaluation following hematopoietic recovery or prolonged cytopenias.

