## **Etoposide**

**Other Names:** Toposar

**Classification:** Podophyllotoxin Derivative

**Mechanism of Action:** Etoposide has been shown to delay transit of cells through the S phase and arrest cells in late S or early G2 phase. The drug may inhibit mitochondrial transport at the NADH dehydrogenase level or inhibit uptake of nucleosides into HeLa cells. It is a topoisomerase II inhibitor and appears to cause DNA strand breaks. Etoposide does not inhibit microtubular assembly.

**Storage and Stability:** Unopened vials of etoposide are stable for 24 months at room temperature (25 degrees Celsius). Vials of etoposide are stable at room temperature for 96

hours when diluted to concentrations of 0.2 milligrams/milliliter (mg/mL); stability is 24 hours with concentrations of 0.4 mg/mL at room temperature. The manufacturer does not recommend that etoposide be administered at concentrations greater than 0.4 mg/mL because time to precipitation is highly unpredictable and precipitate formation has been reported to occur earlier than the utility times listed above. Etoposide 20 mg/ml is stable in a plastic syringe for 5 days when stored at room temperature under fluorescent light.

**Dose Specifics:** Patients will receive etoposide 100 mg/m^2 administered intravenously in 500 ml of 0.9% sodium chloride over 2 hours on days 1-5 (for patients who have elevated total bilirubin, AST or reduced creatinine clearance during the etoposide infusion see treatment schema for dose modification of the etoposide). BSA will be calculated based on actual body weight.

**Preparation:** Etoposide Injection must be diluted prior to use with either 5% Dextrose Injection, or 0.9% Sodium Chloride Injection, to give a final concentration of 0.2 to 0.4 mg/mL . If solutions are prepared at concentrations above 0.4 mg/mL, precipitation may occur. Parenteral drug products should be inspected visually for particulate matter and discoloration prior to administration whenever solution and container permit.

**Route of Administration:** Etoposide should be given as a diluted solution via the IV route.

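### The etoposide hold criterion joins three conditions without grouping and does not match its own heading, so AST above 3 × ULN with CrCl of 50 or more has two opposite instructions

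*Combined protocol and SAP*

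**What the plan says.** The table in Section 8 (treatment schema) is introduced as "Dose modification of etoposide for patients who develop elevated total bilirubin and/or AST or decrease in creatinine clearance". It has three rows:

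- The first covers clearance from 10 up to and including 50 mL/min and reduces the dose to 75%.
- The second covers clearance below 10 mL/min and reduces the dose to 50%.
- The third is the only one that uses liver tests. Its criterion is "CrCl <50 ml/min AND Total bilirubin >3 mg/dL or AST >3 times ULN" and the action given for it is "Hold etoposide".

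Section 9 (Etoposide, Dose Specifics) sends the reader to this table "for patients who have elevated total bilirubin, AST or reduced creatinine clearance during the etoposide infusion". Section 3.1 (Treatment plan) also refers renal and hepatic dose changes to the schema and gives no rule of its own.

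Two other places bear on what a hold means. The scheduling-window row of the Study Flow Chart allows each treatment dose to be delayed by up to 3 days. Section 5.1 makes response evaluability conditional on five days of both mitoxantrone and etoposide in total, and replaces patients who are not evaluable.

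**The concern.** A dose rule that is triggered by laboratory values should give one instruction for each set of values. The hold row does not, because the word order supports two groupings that lead to different actions. The heading adds a second problem: it says a liver abnormality alone is within the table's scope, but no row is defined by a liver value alone.

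The situation is foreseeable. Section 2.1 admits patients with AST up to 2.5 × ULN, so a modest rise crosses 3 × ULN. Section 4.0 requires a daily metabolic panel in hospital, so a crossing on a dosing day will be seen.

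The immediate stake is that etoposide exposure under a stated safety rule is not determined by the protocol. The second is analytic. If a held dose is never given, the grouping could decide whether the patient is evaluable for complete remission under Section 5.1 or is replaced. The plan leaves that open as well.

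**Working it through.** No sample size, power or error rate in the plan rests on this row, so there is no stated figure to reproduce. The check is a truth table.

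**Inputs** (Section 8 table): CrCl 10–50 gives 75%; CrCl below 10 gives 50%; the third row gives hold.

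**Two groupings of the third row**

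- Reading A: CrCl < 50 AND (bilirubin > 3 OR AST > 3 × ULN)
- Reading B: (CrCl < 50 AND bilirubin > 3) OR AST > 3 × ULN

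**Assumptions, neither stated in the table:** hold overrides a percentage row when both match, and a patient who meets no row receives the full dose.

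**Result** (A / B), evaluated at CrCl 80, 50, 40 and 5 mL/min, bilirubin 1 or 4 mg/dL, and AST 1 × or 4 × ULN:

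| CrCl (mL/min) | Neither raised | Bilirubin only | AST only | Both |
|---|---|---|---|---|
| 80 | no row / no row | no row / no row | **no row / hold** | **no row / hold** |
| 50 | 75% / 75% | 75% / 75% | **75% / hold** | **75% / hold** |
| 40 | 75% / 75% | hold / hold | hold / hold | hold / hold |
| 5 | 50% / 50% | hold / hold | hold / hold | hold / hold |

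Three things follow.

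1. The readings differ in 4 of the 16 cells, all with AST above 3 × ULN and CrCl of 50 or more. At exactly 50 the first row applies, so Reading A gives 75% there and not the full dose.
2. Bilirubin above 3 mg/dL alone with CrCl above 50 meets no row under either reading. At exactly 50 the 75% comes from clearance and not from bilirubin.
3. Under Reading A no liver abnormality alone ever changes the dose. Under Reading B the hold row acts as an AST-only rule, but there is still none for bilirubin. Neither reading delivers the scope given in the heading.

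**What a hold means.** The gemtuzumab ozogamicin footnote in the same schema ties its hold to recovery thresholds and sets a latest day. The etoposide row has neither. The flow chart's 3-day allowance suggests that a held dose may be given later, but the table does not refer to it. Section 5.1 asks for a total of five days and does not say that they must be consecutive, nor how held, delayed or reduced doses are counted.

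**The case against.** **The intended grouping is apparent.** The row opens with CrCl, and AND is capitalised while *or* is not, which favours Reading A. That is a fair inference about intent, but conventional operator precedence gives Reading B and the words do not settle it. Reading A is also the one that fits the heading worst. A layout cue may have been lost in the PDF text; if so, it could settle the grouping, but it would not close the bilirubin gap.

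**The heading may only list the variables used.** This is possible. However, it describes patients who develop one abnormality and/or another, and Section 9 repeats the three as alternatives. At the least, the two places and the table need to be reconciled.

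**Practice may be uniform.** Treatment is given on one inpatient service, which may well apply a single interpretation throughout. This stands: the documents do not show that different patients would be dosed under different rules. They also do not show which interpretation would be used.

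**Stronger readings to avoid.** A reader might infer that the choice is between full dose and no dose at all, and that a held patient becomes unevaluable and is replaced. The documents do not support that: with a 3-day delay allowed for each dose and a five-day total required, a held dose may be given later and the patient may remain evaluable. A reader might also want a patient count. The protocol lists raised transaminases in 5% to 20% with mitoxantrone and hepatic toxicity in up to 3% with etoposide, but neither is AST above 3 × ULN during days 1–5. The closest evidence, 35 patients given the same mitoxantrone and etoposide doses and schedule (Section 1.2, Rationale), had no grade 3/4 hepatic toxicity. That points to a low frequency without giving one.

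**Conclusion.** The point holds as an ambiguity and an internal inconsistency in a stated safety rule. For AST above 3 × ULN with CrCl of 50 or more, the hold row supports two opposite instructions: hold, or no hold (unmodified above 50, 75% at exactly 50). For bilirubin above 3 mg/dL alone with CrCl above 50, heading and table disagree on either reading. Sections 3.1 and 9 only point back to the table, so nothing resolves either matter.

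The result rests on the two assumptions given with the truth table. The number of patients affected is unknown, and no effect on the decision rule for 16 and 44 patients is claimed. The link to the primary analysis is limited to this: the plan does not say whether a held dose is delayed or omitted, or whether it counts toward the five days. That counting question also arises for CrCl below 50, where the two readings agree. The wording should be corrected; this review takes no position on which clinical rule is right.

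**What to change.** - Reconcile the Section 8 heading, the table and the Section 9 etoposide text. Write the combined criterion with explicit grouping (brackets or separate rows), so that every combination of CrCl, bilirubin and AST leads to one instruction, including *no change* where that is intended. State which row prevails when two apply. The sponsor decides the content.
- State whether a hold is a delay or an omission, and reconcile it with the 3-day allowance in the Study Flow Chart.
- State in Section 5.1 whether held, delayed or reduced doses count as days received.

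The cost is a wording amendment to one table, its cross-references and one evaluability sentence, plus an update of the pharmacy order set. It needs no extra patients or tests.
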